9. STATISTICAL METHODOLOGY

9.1 General

Data listings will be provided for all data that is databased. Summary statistics and statistical analysis will only be presented for data where detailed in this SAP. For continuous data, summary statistics will include the arithmetic mean, arithmetic standard deviation (SD), median, min, max and N; for log-normal data (e.g. the PK parameters: AUCs and maximum observed drug concentration [C_{max}]) the geometric mean and geometric coefficient of variation (CV%) will also be presented. For categorical data, frequency count and percentages will be presented. Data listings will be provided for all subjects up to the point of withdrawal, with any subjects excluded from the relevant population highlighted. Summary statistics and statistical analyses will generally only be performed for subjects included in the relevant analysis population. For the calculation of summary statistics and statistical analysis, unrounded data will be used.

Mean change from baseline is the mean of all individual subjects' change from baseline values. Each individual change from baseline will be calculated by subtracting the individual subject's baseline value from the value at the timepoint. The individual subject's change from baseline values will be used to calculate the mean change from baseline using a SAS procedure such as Proc Univariate.

Data analysis will be performed using SAS® Version 9.3 or greater.

9.2 Demographics and Subject Disposition

Subject disposition will be listed. The demographic variables age, sex, race, ethnicity, country of enrolment, site ID, body weight, height and body mass index will be summarized and listed.

9.3 Pharmacokinetic Assessment

9.3.1 Pharmacokinetic Analysis

PK parameter estimates will be determined using non-compartmental procedures in validated software program (Phoenix WinNonlin Version 6.4.1 or later).

Plasma concentrations of LY3202626 will be used to determine the following PK parameters, when possible:

Parameter	Units	Definition
AUC(0-t _{last})	ng.h/mL	area under the concentration versus time curve from time zero to time t, where t is the last time point with a measurable concentration
AUC(0-∞)	ng.h/mL	area under the concentration versus time curve from zero to infinity
%AUC(t _{last} -∞)	%	percentage of AUC(0-∞) extrapolated
C _{max}	ng/mL	maximum observed drug concentration
t _{max}	h	time of maximum observed drug concentration
t _{1/2}	h	half-life associated with the terminal rate constant (λ_z) in non-compartmental analysis
CL/F	L/h	apparent total body clearance of drug calculated after extra-vascular administration
V _z /F	L	apparent volume of distribution during the terminal phase after extra-vascular administration
V _{ss} /F	L	apparent volume of distribution at steady state after extra-vascular administration

An alternative AUC measure, such as AUC to a common time point, may be calculated if AUC(0-∞) cannot be reliably calculated.

Additional PK parameters may be calculated, as appropriate. The software and version used for the final analyses will be specified in the CSR. Any exceptions or special handling of data will be clearly documented within the final study report.

Formatting of tables, figures and abbreviations will follow the Eli Lilly Global PK/PD/TS Tool: NON-COMPARTMENTAL PHARMACOKINETIC STYLE GUIDE. The version of the tool effective at the time of PK analysis will be followed.

General PK Parameter Rules

- Actual sampling times will be used in the final analyses of individual PK parameters, except for non-bolus pre-dose sampling times which will be set to zero. For non-bolus, multiple dose profiles, the pre-dose time will be set to zero unless a time deviation falls outside of the protocol blood collection time window which is considered to impact PK parameter derivation.
- C_{\max} and t_{\max} will be reported from observed values. If C_{\max} occurs at more than one time point, t_{\max} will be assigned to the first occurrence of C_{\max} .
- AUC parameters will be calculated using a combination of the linear and logarithmic trapezoidal methods (linear-log trapezoidal rule). The linear trapezoidal method will be applied up to t_{\max} and then the logarithmic trapezoidal method will be used after t_{\max} . The minimum requirement for the calculation of AUC will be the inclusion of at least three consecutive plasma concentrations above the lower limit of quantification (LLOQ), with at least one of these concentrations following C_{\max} . AUC(0- ∞) values where the percentage of the total area extrapolated is more than 20% will be flagged. Any AUC(0- ∞) value excluded from summary statistics will be noted in the footnote of the summary table.
- Half-life ($t_{1/2}$) will be calculated, when appropriate, based on the apparent terminal log - linear portion of the concentration-time curve. The start of the terminal elimination phase for each subject will be defined by visual inspection and generally will be the first point at which there is no systematic deviation from the log -linear decline in plasma concentrations. Half-life will only be calculated when a reliable estimate for this parameter can be obtained comprising of at least 3 data points. If $t_{1/2}$ is estimated over a time window of less than 2 half-lives, the values will be flagged in the data listings. Any $t_{1/2}$ value excluded from summary statistics will be documented in the footnote of the summary table.
- A uniform weighting scheme will be used in the regression analysis of the terminal log - linear portion of the concentration-time curve.
- The parameters based on observed last quantifiable drug concentration (C_{last}) will be reported.

Individual PK Parameter Rules

- Only quantifiable concentrations will be used to calculate PK parameters with the exception of special handling of certain concentrations reported below the lower limit of quantitation (BQL). Plasma concentrations reported as BQL will be set to a value of zero when all of the following conditions are met:
 - The compound is non-endogenous.

- The samples are from the initial dose period for a subject or from a subsequent dose period following a suitable wash-out period.
- The time points occur before the first quantifiable concentration.
- All other BQL concentrations that do not meet the above criteria will be set to missing.
- Also, where two or more consecutive concentrations are BQL towards the end of a profile, the profile will be deemed to have terminated and therefore any further quantifiable concentrations will be set to missing for the calculation of the PK parameters unless it is considered to be a true characteristic of the profile of the drug.

Individual Concentration vs. Time Profiles

- Individual concentrations will be plotted utilizing actual sampling times.
- The terminal point selections will be indicated on a semi-logarithmic plot.

Average Concentration vs. Time Profiles

- The average concentration profiles will be graphed using scheduled (nominal) sampling times.
- The average concentration profiles will be graphed using arithmetic average concentrations.
- The pre-dose average concentration for single-dose data from non-endogenous compounds will be set to zero. Otherwise, only quantifiable concentrations will be used to calculate average concentrations.
- Concentrations at a sampling time exceeding the sampling time window specified in the protocol, or $\pm 10\%$, will be excluded from the average concentration profiles.
- Concentrations excluded from the mean calculation will be documented in the final study report.
- A concentration average will be plotted for a given sampling time only if 2/3 of the individual data at the time point have quantifiable measurements that are within the sampling time window specified in the protocol or $\pm 10\%$. An average concentration estimated with less than 2/3 but more than 3 data points may be displayed on the mean concentration plot if determined to be appropriate and will be documented within the final study report.

Treatment of Outliers during Pharmacokinetic Analysis

Application of this procedure to all PK analyses is not a requirement. Rather, this procedure provides justification for exclusion of data when scientifically appropriate. This procedure describes the methodology for identifying an individual value as an outlier for potential exclusion, but does not require that the value be excluded from analysis. The following methodology will not be used to exclude complete profiles from analysis.

Data within an Individual Profile

A value within an individual profile may be excluded from analysis if any of the following criteria are met:

- For PK profiles during multiple dosing, the concentration of the pre-dose sample exceeds all measured concentrations for that individual in the subsequent post-dose samples.
- For PK profiles during single dosing of non-endogenous compounds, the concentration in a pre-dose sample is quantifiable.
- For any questionable datum that does not satisfy the above criteria, the profile will be evaluated and results reported with and without the suspected datum.

Data between Individual Profiles

1. If $n < 6$, then the dataset is too small to conduct a reliable range test. Data will be analyzed with and without the atypical value, and both sets of results will be reported.
2. If $n \geq 6$, then an objective outlier test will be used to compare the atypical value to other values included in that calculation:
 - a. Transform all values in the calculation to the logarithmic domain.
 - b. Find the most extreme value from the arithmetic mean of the log transformed values and exclude that value from the dataset.
 - c. Calculate the lower and upper bounds of the range defined by the arithmetic mean $\pm 3*SD$ of the remaining log-transformed values.
 - d. If the extreme value is within the range of arithmetic mean $\pm 3*SD$, then it is not an outlier and will be retained in the dataset.
 - e. If the extreme value is outside the range of arithmetic mean $\pm 3*SD$, then it is an outlier and will be excluded from analysis.

If the remaining dataset contains another atypical datum suspected to be an outlier and $n \geq 6$ following the exclusion, then repeat step 2 above. This evaluation may be repeated as many times as necessary, excluding only one suspected outlier in each iteration, until all data remaining in the dataset fall within the range of arithmetic mean $\pm 3*SD$ of the log-transformed values.

Reporting of Excluded Values

Individual values excluded as outliers will be documented in the final report. Approval of the final report will connote approval of the exclusion.

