10.3. Statistical Analyses

Statistical analysis of this study will be the responsibility of Eli Lilly and Company or its designee.

Pharmacokinetic analyses will be conducted on the full analysis set. This set includes all data from all subjects receiving at least 1 dose of LY3202626, according to the dose administration the subjects actually received. Safety analyses will be conducted for all enrolled subjects, whether or not they completed all protocol requirements.

Additional exploratory analyses of the data will be conducted as deemed appropriate. Study results may be pooled with the results of other studies for population PK analysis purposes to avoid issues with post-hoc analyses and incomplete disclosures of analyses.

No adjustments for multiple comparisons will be made.

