8. DEFINITION OF ANALYSIS POPULATIONS

The "Safety" population will consist of all enrolled subjects, whether or not they completed all protocol requirements.

The PK analyses will be conducted on the full analysis set. This set includes all data from all subjects who received at least one dose of LY3202626.

The "Pharmacodynamic" population will consist of all subjects who received at least one dose of study drug and have evaluable PD data.

All protocol deviations that occur during the study will be considered for their severity/impact and will be taken into consideration when subjects are assigned to analysis populations.

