9.3.2 Pharmacokinetic Parameter Estimation

The primary parameters for analysis, C_{max} , $AUC(0-\infty)$, $AUC(0-t_{last})$, and t_{max} of LY3202626, will be evaluated to delineate relative bioavailability and food effects.

The following comparisons will be interests of statistical analysis of PK parameters:

- relative bioavailability: LY3202626 T1-12 fasted (test) versus LY3202626 R fasted (reference)
- food effect: LY3202626 T1-12 fed (test) versus LY3202626 T1-12 fasted (reference).

Log-transformed C_{max} and AUC estimates will be evaluated in a linear mixed -effects model with fixed effects for dose administration and period and a random effect for subject. The ratio of geometric least squares means and corresponding 90% CI will be presented for LY3202626 T1-12 versus LY3202626 R for analysis of relative bioavailability, and LY3202626 T1 -12 administered with a high-fat meal versus LY3202626 T1-12 administered fasted for the analysis of the food effect. One model will be used for the assessment of relative bioavailability and the effect of food.

The t_{max} will be analyzed non-parametrically for the same comparisons stated above. Median of differences and approximate 90% CI for the median of differences will be calculated. P-values will also be calculated using a Wilcoxon signed rank test.

Additional analyses may be performed if deemed necessary.

Example SAS code:

```
proc mixed data=test covtest alpha=0.1;
  class treatment period subject;
  model log_pk = treatment period / ddfm=kr alpha=0.1;
  random subject;
  lsmeans treatment / pdiff cl alpha=0.1;
  ods output lsmeans=lsmeans;
  ods output diffs=diffs;
  ods output covparms=cov;
run;
```

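### A PK profile cut short by withdrawal or missed visits in Period 2 or 3 still gives an AUC(0-tlast) that enters the primary model against the same subject's full 168 h profiles

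*SAP*

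**What the plan says.** - **Endpoint.** AUC(0-tlast) is one of the primary parameters (SAP 9.3.2; Protocol 10.3.2.1). SAP 9.3.1 defines it as "area under the concentration versus time curve from time zero to time t, where t is the last time point with a measurable concentration". It ends at each profile's own last measurable sample, not at a common time.
- **Entry rule.** SAP 9.3.1: "The minimum requirement for the calculation of AUC will be the inclusion of at least three consecutive plasma concentrations above the lower limit of quantification", with at least one value after Cmax. No sampling duration is required.
- **Analysis set.** SAP 8: "This set includes all data from all subjects who received at least one dose of LY3202626". Protocol 10.3: "This set includes all data from all subjects receiving at least 1 dose of LY3202626, according to the dose administration the subjects actually received". Neither sets a completeness condition.
- **Model.** SAP 9.3.2 fits one mixed model to the log parameters "with fixed effects for dose administration and period and a random effect for subject", and takes 90% intervals from "lsmeans treatment / pdiff cl alpha=0.1". Nothing in it reflects profile length.
- **Nearest safeguard.** SAP 9.3.1: "An alternative AUC measure, such as AUC to a common time point, may be calculated if AUC(0-∞) cannot be reliably calculated". This is optional and is triggered by AUC(0-∞). The flag at more than 20% extrapolated area also concerns AUC(0-∞) only.
- **Schedule.** Subjects may leave the unit after the 24 h or 36 h procedures and then attend daily as outpatients to 168 h (Protocol 5.1; SAP 5).

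**The concern.** tlast can be early for two different reasons: the drug has fallen below quantification, or nobody took the later samples. The rules treat these alike. A subject who completes Period 1 on the capsule and is last sampled at 24 h on the fasted tablet contributes a valid AUC(0-24) and a valid AUC(0-168). The model reads the difference between them as a formulation effect.

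The direction depends on which profile is cut:

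- A cut fasted-tablet profile lowers tablet/capsule and raises fed/fasted.
- A cut capsule profile raises tablet/capsule.
- A cut fed profile lowers fed/fasted.

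The extra discrepancy also inflates the residual variance and so the 90% CI. The results are meant to inform dose selection and whether the tablet can be taken without regard to food (Protocol 3.1). The sample size rests on precision of the AUC ratio (Protocol 10.1; SAP 7).

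**Working it through.** **The plan's own figures.** The sample-size calculation cannot be reproduced because its CV and precision inputs are redacted. The counts agree: 24 − 20 = 4 non-completers allowed (4/24 = 16.7%), and 24 + 6 = 30. There are 19 sampling times per period; 19 × 3 = 57, plus 2 = 59, as in the blood sampling table (Protocol Appendix 4).

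**Inputs from the documents.** Sampling times (Protocol 2); tmax about 4 h (Protocol 3.2); linear trapezoid to tmax and logarithmic after it (SAP 9.3.1); six sequences (SAP 5); model (SAP 9.3.2); 24 subjects.

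**Assumptions, not in the documents.** One compartment; half-life 10, 20 or 40 h; within-subject CV about 20%; between-subject log SD 0.35 to 0.4; true ratios of 1.00.

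**Step 1: share of AUC(0-168) captured.** C(t) ∝ exp(−ke·t) − exp(−ka·t), with ke = ln 2 / half-life and ka chosen so that ln(ka/ke)/(ka − ke) = 4 h.

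| Last sample | 10 h | 20 h | 40 h |
|---|---|---|---|
| 24 h | 79% | 55% | 35% |
| 36 h | 91% | 70% | 48% |
| 48 h | 96% | 80% | 59% |
| 144 h | 100% | 99.6% | 97% |

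**Step 2: effect on the ratios.** With 24 subjects, one log-AUC changed by ln f moves the affected treatment mean by (1/24)·ln f, so the ratio becomes about f^(1/24):

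- 0.786^(1/24) = 0.990
- 0.547^(1/24) = 0.975
- 0.348^(1/24) = 0.957

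Fitting the SAP model by generalised least squares gives the same values. For cuts at 24 h and half-lives of 10 / 20 / 40 h:

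| Profile cut | Tablet/capsule | Fed/fasted |
|---|---|---|
| One fasted tablet, Period 2 (sequence ABC) | 0.990 / 0.975 / 0.957 | 1.006 / 1.014 / 1.025 |
| Three fasted tablet, Periods 2 and 3 | 0.970 / 0.927 / 0.876 | 1.026 / 1.065 / 1.117 |
| One capsule, Period 3 | 1.010 / 1.025 / 1.045 | 1.000 |
| One fed tablet, Period 3 | 1.000 | 0.990 / 0.975 / 0.957 |
| One fasted tablet, Period 1, nothing later | 0.998 / 0.995 / 0.991 | 1.002 / 1.005 / 1.009 |

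Two fasted-tablet profiles at 35% capture give 0.348^(2/24) = 0.916 if both subjects had already taken the capsule, and about 0.93 if one had not.

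**Step 3: effect on the interval (simulated REML fits).**

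- One profile at 57% capture: log-scale width 0.193 to 0.202, about 5% wider.
- One profile at 35%: 0.190 to 0.217, about 14% wider.
- Two profiles at 35%: about 25 to 30% wider.

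**Step 4: leaving the cut value out.** The ratio returns to 1.000. Relative to complete data, the interval is about 2% wider with one value left out (0.190 to 0.194) and about 5% wider with three (0.193 to 0.203).

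**Step 5: what a 20% tail threshold would let through.** A retained profile holds at least 80% of its area, so one such profile shifts the ratio no further than 0.80^(1/24) = 0.991.

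**The case against.** **Truncation is already visible in the plan.** A 24 h stop at a 20 h half-life leaves about 45% of AUC(0-∞) extrapolated, which is flagged. The terminal window is then at most 24 − 4 = 20 h, under two half-lives, which is also flagged. That opens the optional common-time AUC. SAP 8 weighs protocol deviations when assigning populations, and SAP 9.3.2 allows additional analyses. All of this stands as mitigation. None of it is a rule about AUC(0-tlast), and in an open-label study the choice would be made with the values in view.

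**The outlier procedure might remove the value.** It is optional and never requires exclusion. Simulated with n = 21, it catches a profile at 57% capture in 46%, 17% or 9% of cases when the CV of the values tested is 20%, 30% or 40%. At 36% capture the figures are 97%, 68% and 39%. It is not a dependable safeguard.

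**One compartment is pessimistic.** Protocol 3.2 describes multiexponential elimination, which puts more of the area early. With assumed early half-lives of 4 to 6 h carrying 50 to 85% of the disposition amplitude, capture at 24 h is 61 to 77% at a 20 h terminal half-life and 40 to 61% at 40 h. By f^(1/24), one profile then gives 0.980 to 0.989 and 0.963 to 0.980. So the shares in Step 1 are a low bound on capture, and the shifts are towards the upper end.

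**Exposure is narrow.** A reader might take 24 enrolled for 20 completers to mean that about four profiles will be cut. The documents do not say so: the allowance covers all non-completion. Leaving between periods truncates nothing, and a Period 1 leaver hardly matters.

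**Cmax.** Because Cmax and tmax "will be reported from observed values" with no post-peak condition, a reader might extend the point to them. Subjects are resident until the 24 h procedures and Cmax comes at about 4 h, so this would need an exit from the unit within hours of dosing. It is too remote to need a rule.

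**Conclusion.** The gap is real. Followed as written, the plan puts withdrawal-truncated AUC(0-tlast) values into the primary comparison, and no passage prevents it. The mechanism is certain from the text. The size is not, because half-life and CV are redacted.

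Under the stated assumptions, one fasted-tablet profile cut at 24 h in Period 2 or 3 moves a true tablet/capsule ratio of 1.00 to about 0.99, 0.975 or 0.96. The 90% CI is about 5% wider at 56% capture and 15% wider at 35%. Two profiles at 35% give about 0.92 to 0.93 and a CI 25 to 30% wider. This affects one of the primary parameters, and the visible text states no equivalence margin, so the point is worth fixing but does not threaten the study.

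Two stronger readings are not supported:

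- **That the rule works against the tablet.** The loss falls on whichever treatment was being taken, and a cut capsule profile favours the tablet.
- **That the CI widens by 30% or more for a single leaver.** Paired differences would suggest this, but the SAP specifies a mixed model over three treatments, which gives about half that.

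**What to change.** Add to SAP 9.3.1 and 9.3.2, before analysis:

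- Where the last sample obtained is quantifiable, later scheduled samples were not taken, and the missing tail is material, AUC(0-tlast) is listed and flagged but not entered in the AUC(0-tlast) model. Material could mean that %AUC(tlast-∞) exceeds the SAP's existing 20% flag or cannot be reliably estimated.
- Profiles missing only late samples with a small tail are kept. Without this limit the rule would discard a profile lacking only the 168 h sample, which holds 99.6% or 97% of the area at a 20 or 40 h half-life.
- A supporting analysis uses AUC to the last time point common to the subject's compared periods.
- Results are reported with and without the excluded values.
- SAP 11, which now declares no changes, records the departure from the protocol's all-data PK set.

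No new data or procedures are needed. The cost is a few non-completer values leaving one model, with a CI about 2 to 3% wider than complete values would give for one or two exclusions and about 5% for three. No change to the Cmax or tmax rules is proposed.

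### Does letting a quantifiable pre-dose concentration be dropped in Periods 2 and 3, with the rest of the profile kept, put the primary comparison at risk?

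*SAP*

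**What the plan says.** The outlier procedure in SAP 9.3.1 is optional. Its lead-in reads "A value within an individual profile may be excluded from analysis if any of the following criteria are met", and the criterion that fits this study is "For PK profiles during single dosing of non-endogenous compounds, the concentration in a pre-dose sample is quantifiable". It names no period. The procedure works on single values: "The following methodology will not be used to exclude complete profiles from analysis". Paired results are promised for other cases only: "For any questionable datum that does not satisfy the above criteria, the profile will be evaluated and results reported with and without" the suspected value. On disclosure, "Individual values excluded as outliers will be documented in the final report".

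Three neighbouring rules in the same section matter:

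- For BQL values before the first quantifiable one, zero is imputed in the first dose period or when the sample is "from a subsequent dose period following a suitable wash-out period". No test of suitability is given.
- For AUC, "The linear trapezoidal method will be applied up to" tmax, with the logarithmic rule after it.
- For mean-profile graphs, "The pre-dose average concentration for single-dose data from non-endogenous compounds will be set to zero".

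Protocol 5.4 relies on a half-life that is redacted in the public copy to conclude that at least 10 days between doses prevents carryover. The model in SAP 9.3.2 has treatment, period and subject terms only.

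**The concern.** Exclusion criterion 13 (Protocol 6.2) keeps out anyone already exposed to the drug. A quantifiable pre-dose value in Period 1 therefore points to a sample or assay fault. In Period 2 or 3 the same finding is the most direct sign that the previous dose has not washed out. One rule treats both as a removable oddity, and the second kind can be removed without a paired result.

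Removing it also cures nothing. Any residual drug is still present in every later sample of that profile, so it stays in Cmax and AUC. If carryover differed by formulation or food state, or if dropout left the sequences uneven, the tablet/capsule and fed/fasted ratios could be biased, and no sensitivity result is planned to show it.

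**Working it through.** The plan states no figure on this point, so there is none to reproduce.

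**Inputs from the documents.** At least 10 days (240 h) between doses, in six sequences (Protocol 5.1). PK samples at predose, 0.5 h and onward to 168 h, 19 per period (Protocol 2); 19 × 3 + 2 = 59 agrees with Appendix 4, so a pre-dose sample exists in every period. Cmax at about 4 h (Protocol 3.2). AUC rule and model as in SAP 9.3.1 and 9.3.2.

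**Assumptions.** The half-life is redacted, so 24–100 h is examined. Two models are used: (a) one compartment with tmax 4 h; (b) two-phase disposition with absorption half-life 1 h, distribution half-life 8 h and the terminal phase at 10–30% of amplitude. Within-subject CV is taken as 20%.

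**Step 1: what the exclusion does.** The first trapezoid is 0.5 × (C0 + C0.5)/2 = 0.25 × (C0 + C0.5). The SAP does not say whether a removed value is then set to zero, so both cases are taken.

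- Set to zero, the loss is 0.25 × C0. In model (a) this is 0.012% of AUC(0-tlast) at a 48 h half-life, 0.027% at 72 h and 0.039% at 96 h. Model (b) also stays below 0.04%.
- Removed without back-filling, the whole trapezoid is lost, about 0.2–0.5% of AUC.
- Cmax is unaffected, because the maximum is not at time zero.

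**Step 2: how large carryover could be.** The inflation is the previous dose's residual area divided by the area from the new dose.

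| Assumed half-life | Half-lives in 240 h | Model (a), AUC(0-tlast) | Model (b), AUC(0-∞) |
|---|---|---|---|
| 24 h | 10 | 0.1% | – |
| 30 h | 8 | – | 0.1–0.3% |
| 36 h | 6.7 | 1.0% | – |
| 48 h | 5 | 3.2% | 1.3–2.3% |
| 60 h | 4 | – | about 3–5% |
| 72 h | 3.3 | 10.0% | – |
| 96–100 h | 2.5–2.4 | 17.8% | about 11–16% |

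**Step 3: what reaches the ratio.** With the six sequences equally filled, two thirds of each treatment's observations fall in Periods 2 and 3, half of them after each of the other two treatments.

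- *Equal carryover* adds the same amount to every treatment mean and cancels.
- *Unequal carryover*, for example 6% after the fasted tablet and 3% after the others. The fasted tablet receives (3 + 3)/2 = 3% and the capsule (6 + 3)/2 = 4.5%. The shift in tablet/capsule is (2/3) × (3 − 4.5) = −1.0%, and in fed/fasted +1.0%.
- *Carryover as a fraction c of the preceding exposure*, true tablet/capsule ratio 1.25, no food effect. The log shift is (2/3) × {[ln(1 + 0.8c) + ln(1 + c)]/2 − ln(1 + 1.25c)}. At c = 0.023 this is (2/3) × (0.0205 − 0.0283) = −0.0052, so 1.25 is estimated as 1.243. At c = 0.032 it is 1.241, at 0.05 it is 1.236 and at 0.16 it is 1.211.
- *Three slow eliminators among 20 completers*, placed at random over the sequences. At +16% in both later periods the mean shift is 0, the mean absolute shift is 0.8%, and it exceeds 1% in 27% of placements and 2% in 5%. At +5% it never exceeds 1%.

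**Step 4: scale.** On the log scale the SD is √ln(1 + 0.2²) = 0.198. With 20 subjects and 38 degrees of freedom the 90% half-width is 1.686 × 0.198 × √(2/20) = 0.106, a CI factor of about 1.11. The shift from 1.25 to 1.243 is a factor of 0.995.

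**The case for a change.** The best case for a change is that the SAP demands paired results for miscellaneous odd values but not for the one value that tests the crossover's main assumption. The safeguards can also miss it. At a 60 h half-life, 120 h of the 168 h window satisfies the two-half-life check, and only about 7–11% of AUC is extrapolated, below the 20% flag. Balance is not assured: 20 completers cannot divide evenly over six sequences, and the full analysis set keeps partial data. In an open-label study, an analysis fixed in advance is better than one chosen after the data are seen.

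The reading of the text stands, and so does the absence of a pre-specified carryover analysis. The rest does not carry the point. By Step 1, paired results for the pre-dose value would show almost nothing, and confining the criterion to Period 1 would change no estimate. The zero in the mean profile affects a graph only.

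What is left is a request for a different analysis: refitting the model without the affected subject-periods. Its trigger has no basis in the documents. Under model (b), a limit of 5% of Cmax would miss AUC inflation of up to 14.5%, and a limit of 1% would miss a little over 3%. Dropping every later profile with any quantifiable pre-dose value could leave little more than a parallel comparison of Period 1. Either version selects subjects by slow elimination and unbalances the sequences it is meant to protect. On dropout, Protocol 10.1 gives each replacement the withdrawn subject's sequence, which limits the imbalance.

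**Conclusion.** No change is needed. The rule is loosely worded for a crossover, but following it does not give a worse estimate: its own effect is under 0.04% of AUC if the point is zeroed, about 0.2–0.5% if the first trapezoid is lost, and nothing on Cmax.

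Harm would need carryover that the documents do not show. Protocol 5.4 concludes that there is none. If that rests on the customary five half-lives (an assumption, since the value is redacted), the half-life is 48 h or less, AUC inflation is at most about 2–3%, and a true ratio of 1.25 is still estimated as about 1.24. Neither document sets an equivalence limit that a shift of this size could cross. Larger effects need a half-life of roughly 60 h or more together with carryover that depends on treatment or exposure, or an unlucky placement of slow eliminators.

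The gap is also one that analysts can fill sensibly. SAP 9.1 lists all databased data, 9.3.1 plots individual profiles and has exclusions reported, and 9.3.2 leaves room for further analyses. If later-period pre-dose values proved quantifiable to a degree that mattered, they would be visible by period and the model could be refitted then. The conclusion rests on the assumed half-life range, the two PK models and roughly equal filling of the six sequences.
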